We will conduct a hybrid type III effectiveness-implementation trial with a longitudinal cluster randomized design to answer questions related to implementation strategy and program effectiveness. We will also apply mixed methods to investigate implementation strategy mechanisms. During the active implementation period, all 30 clinics in the two participating health systems will receive *SAFE Firearm* materials, including brief training in program delivery, cable locks, and the deployment of an EHR implementation strategy. Half of the clinics will be randomized to only receive the EHR implementation strategy (*Nudge*); the other half will be randomized to receive *Nudge* plus 1 year of facilitation to target additional clinician and organizational implementation barriers (*Nudge+*). We will

collect the primary implementation outcome for 1 year following the active trial year to allow for comparisons between the active and sustainment periods. Results will guide future efforts to promote firearm safety as a universal suicide prevention strategy.

EQUITY SUPPLEMENT PURPOSE:

Prior to launching the full trial, we are piloting the delivery of the *SAFE Firearm* program in 2 clinics in each health system during an approximately 4-5 month period. Pilot procedures will mirror the procedures described in the protocol and use the same parent survey instrument (more details are below). After the pilot, we will conduct this sub-study. Specifically, we will explore any signals of disparities and examine *SAFE Firearm* delivery by children's medical complexity (per ICD-9 and -10 codes) and race/ethnicity. Because we anticipate that clinicians will provide helpful contextualization for the program that will be informative for facilitation for the program and for the broader literature on firearm safety counseling, regardless of whether we detect differences in program delivery, we will interview KPCO and HFH clinicians who participated in the pilot to identify specific delivery barriers, and convene key stakeholders (e.g., facilitation leaders, pediatric leadership) for virtual meetings. We expect that this step will prime facilitation for trial launch. The goal of this sub-study is to learn more about barriers to delivering the *SAFE Firearm* program equitably to all patients, regardless of medical complexity and race/ethnicity, and to optimize facilitation to address disparities.

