Primary outcome variables:

- Aim 1. Clinician-reported reach (program delivery as documented in the EHR)
- Aim 2. Staff-reported clinic adaptive reserve
- Aim 3. Parent-reported firearm storage behavior

Secondary/Other outcome variables (Moderators and mediators to be measured):

- Aim 1. Parent-reported clinician fidelity, cable lock distribution, acceptability, cost
- Aim 2.
 - Moderators: Clinician burnout, clinician attitudes towards firearms counseling
 - Mediators: Clinician motivation
- Aim 3. Youth suicide attempts, deaths, and unintentional firearm injury and mortality

BACKGROUND:

Youth suicide deaths are on the rise in the United States (U.S.). Firearms are a common and lethal method of suicide attempt. Reducing access to lethal means is a promising yet underused suicide prevention strategy.²⁷ Firearms are a critical target of such efforts^{28,29} given that they are present in one in three U.S. homes and these numbers are increasing in the wake of Covid-19.³⁰ Recent research has found that only 3 in 10 firearm-owning families with children store all guns in their home in the safest manner: locked and unloaded. Approximately 4.6 million U.S. children (7%) live in homes in which at least one firearm is stored unlocked and loaded.³¹ Given that the presence of firearms in the home is a robust risk factor for suicide,³² safe storage of firearms in the home is imperative for reducing youth suicide attempts and death. Simulation research has found that even a modest increase in safe firearm storage could prevent as many as 32% of youth firearm deaths due to suicide and accidents.¹⁶ Thus, efforts to increase implementation of interventions to improve safe storage could save young lives nationally.

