 - For the EHR/Administrative data extraction (i.e., which includes data from the EHR, VDW, and Administrative systems; see **Data Collection** section for more details), we anticipate HFH and KPCO to pull data from 74,080 unique clinic encounters each year (based on health system numbers from 2018). As such, we anticipate extracting data from about 37,040 clinic encounters in the 6-month pre-implementation period, 74,080 clinic encounters in the 1-year implementation period, and 74,080 clinic encounters in the 1-year sustainment period. In order to make this number we will pull approximately 100,000 from KPCO and 100,000 from HFH.
 - For the parent surveys, we will recruit eligible participants from the extracted EHR/Administrative data each study period. We estimate a 31.58% response rate, with our main goal of 23,394 surveys during the 1-year implementation period. We also hope to conduct 11,697 surveys in the 6-month pre-implementation period and 23,394 surveys in the 1-year sustainment period.

Study Phase	Pre-implementation (6 mo)	Implementation (1 yr)	Sustainment (1 yr)	Total maximum enrollment
EHR/Admin data	37,040	74,080	74,080	185,200 ¹
Survey data (31.58% response rate) ²	11,697	23,394	23,394	58,485 ¹

¹This is the total maximum enrollment (i.e. if all data came from unique patients at each period)

²The participants who complete the surveys will be identified from the EHR/Admin data above

- **Primary Care Providers (PCPs).** There are currently 137 pediatric physicians and 14 non-physician PCPs (N = 151) in the two systems. Two surveys will be administered to these PCPs: one during the 6-month pre-implementation period (baseline survey) and one during the 1-year active implementation period (implementation survey). We expect response rates of 50% at each of these two time points, so our target

accrual for surveys is **151 PCPs**. We will also purposively sample 16 of these PCP survey respondents to participate in a one-time qualitative interview.

- **Equity Supplement.** We plan to identify up to 12 clinicians who engaged in the pilot at either Henry Ford Health or Kaiser Permanente Colorado for qualitative interviews. The key attendees for our stakeholder meeting will include [name] and KPCO and HFH Site PIs (N=3), facilitation leaders (N=6), and pediatric leadership (N=4). Note, we are not conceptualizing the stakeholder meeting as a research activity.

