- Aim 1 measures will ask questions about PCP fidelity to the two steps of the *SAFE Firearm* program (whichever question was not answered during Part 1; e.g. did your child's PCP talk to you about firearm safety, did your child's PCP offer you a cable lock?). Aim 1 measures may also include questions about acceptability of the *SAFE Firearm* program and parents' reactions to the firearm discussions with providers.
- Aim 3 measures will ask questions about firearm storage behavior (e.g. if they took a cable lock, if all firearms are stored with a gun lock on them, if bullets are stored separate from all firearms, etc.).
- For NIH reporting purposes, we will also collect parent demographics (e.g., gender, race, ethnicity); disclosure of this information will be optional.

- **PCP surveys (Aims 1 and 2).** We anticipate PCP surveys will take about 15 minutes for PCPs to complete. Two surveys will be administered: one will be completed during the 6-month pre-implementation period (baseline survey) and one will be completed during the 1-year active implementation period. Each of the surveys will include questions related to some or all of the following constructs below:
 - Aim 1 measures will ask questions about acceptability and use of the *SAFE Firearm* program and of the implementation strategies. PCPs will also be offered the opportunity to disclose whether they are firearm owners; we will make it clear that disclosure is entirely voluntary.
 - Aim 2 moderator measures will ask questions about PCP attitudes and experiences (e.g., attitudes towards firearm counseling, burnout).
 - Aim 2 mediator measures will also ask about PCP attitudes and experiences (e.g., clinic-level adaptive reserve and PCP motivation to implement *SAFE Firearm*).
 - Demographic questions
- **PCP, Point People, and Leader interviews (Aim 2).** We anticipate interviews with PCPs, point people, and leaders will last about 15-30 minutes. These interviews will be administered once, during the end of active implementation through the early part of the sustainment period. Development of the interview guide was guided by the Consolidated Framework for Implementation Research (CFIR); the guide asks questions about other additional mechanisms through which implementation strategies might operate (e.g. clinician knowledge about firearms, community factors outside the clinic).

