- **Aim 1 Analysis.** Our power analyses are based upon the primary implementation outcome of reach, consistent with best practices for hybrid type III trials.⁶¹ All other implementation outcomes are secondary. Our sample sizes for the project are determined by the fixed number of parent-youth dyads, PCPs, and pediatric clinics within our two health systems. Data are clustered within health system, clinic, and PCP. We expect that approximately 48,475 parents of youth will be eligible to participate each year, and expect to include data from 151 PCPs, within 41 clinics. Therefore, we anticipate obtaining EHR reach data for 48,475 patients during the one-year active implementation period. We base our power calculations on our study design and prior research from our group demonstrating that current PCP use of the *SAFE Firearm* program components are 28% for brief counseling on safe firearm storage and 2% for offering cable locks.¹⁴ We used the PASS power calculation program,⁶² assuming an estimate of an ICC of .07 for explained variance among both PCPs and clinics,⁶³ and conclude that we will have 80% power to detect small effects of the less intensive implementation condition (*Nudge*) on reach (Cohen's d = 0.25 and 0.29, respectively).⁶⁴ Alpha is set at .05 (two-tailed). A small to moderate effect is reasonable to expect based on prior research demonstrating that EHR nudges using active choice approaches produce effects in this range.⁵¹ Because the clinics will be our unit of randomization, it was not necessary to account for the health system ICC in the power analysis. We will account for any differences between health systems by weighting health system the strongest in our covariate constrained randomization. Also, we will conduct a sensitivity analysis that controls for health system as a fixed effect in our analyses and will explore whether intervention effectiveness varies significantly by health system. Our approach is consistent with similar work that has been published in leading medical journals (i.e., Navathe et al., 2019, *JAMA*, Sharma et al., 2019, *JAMA Oncology*). In Aim 1, the primary dependent variable is reach. For each observation period (active implementation, sustainment) and for each implementation condition (*Nudge*, *Nudge+*), we will describe the proportion of clinicians who reported having delivered the program with EHR reach. We will calculate EHR reach using three binary outcomes: received counseling (yes/no), offered lock (yes/no), both (yes/no). We will then conduct separate models. In the first set of models, we will examine whether the odds of receiving components of *SAFE Firearm* increased more in the *Nudge+* group compared with the *Nudge* group between the active implementation and sustainment periods. The fixed effects in the model will include implementation condition (*Nudge*, *Nudge+*), time (active implementation, sustainment), and their interaction; the magnitude and statistical significance of the parameter estimate for the interaction term will be of primary interest. Given the nested data (i.e., parent-youth dyads nested within PCPs; PCPs nested within clinics; clinics nested within health systems), analyses will rely on 3-level logistic mixed effects regression models for reach as a dichotomous implementation outcome.^{65,66} Linear mixed effects regression will be used to model continuous secondary outcomes (e.g., acceptability). For all models, our independent variable of interest will be a binary

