- **Aim 2 Analysis.** *Quantitative analysis.* For our 2-2-1 mediation analyses, we will have approximately 76 PCPs and 20 clinics per study arm. Using the PASS power calculation program,⁶² we anticipate these sample sizes will yield sufficient power to detect a moderate indirect effect (Cohen's $d = .44$) through the clinic-level mediator (i.e., clinic adaptive reserve). We assume there will be a large effect of the strategy on the mediator and of the mediator on the outcome based on previous research.⁶⁸ This is a conservative estimate because the calculation does not account for the additional power that will be gained due to the two measurement time-points for each PCP. We will conduct exploratory analyses to investigate motivation as a mediator. Mediation will be tested using the product of coefficients approach for multilevel mediation analysis,⁶⁹⁻⁷¹ which we have used in previous studies.⁷² In this approach, the total effect of the implementation strategy is parsed into direct and indirect effects associated with the mediator. We will test each mechanism in a separate 2-2-1 mediation model. Path "a" represents the effect of the implementation strategy (*Nudge, Nudge+*) at the clinic level on the clinic-level mediator (i.e., clinic adaptive reserve). Path "b" represents the relationship between the clinic-level mediator (i.e., adaptive reserve) and the three binary reach outcomes (counseling, cable lock, both). We will calculate change in reach for each of the two time-points using the 6 month period preceding each survey administration. An unbiased estimate of the mediated effect is derived via the product of the "a" and "b" paths (i.e., $a \times b$) from these analyses.^{70,71,73} We will test the statistical significance of the mediated effects using the joint significance test.⁷⁴ We will use Monte Carlo simulation methods to derive confidence intervals.⁷⁴⁻⁷⁷ We will repeat this model for our exploratory mediator, motivation. Moderators of the strategies' effects will be tested separately by adding terms for each moderator and its interaction with the implementation strategy to the Aim 1 models only during the active implementation period. These models will estimate the conditional relationships between the implementation strategies and implementation outcomes across different values of the putative moderators. *Qualitative analysis and mixed methods.* Text answers from open-ended questions with parents from Aim 1, and digitally recorded and transcribed interviews with PCPs, point people, and leaders on the mechanisms of the implementation strategies, will be loaded into NVivo qualitative data analysis software. Analysis will be led by the research team guided by an integrated approach,⁷⁸ which outlines a rigorous, systematic method for analyzing qualitative data using an inductive and deductive process of iterative coding to identify recurrent themes, categories, and relationships. We will ensure at least 80% interrater reliability amongst our coders (we will have at least two). The structure of our mixed methods approach is sequential (quantitative data is collected before qualitative data and quantitative data is weighed more strongly than qualitative; QUAN>qual). The function is of complementarity (to elaborate upon the quantitative findings to understand the *how* of implementation), and the process is connecting (having the qualitative data set build upon the quantitative data set).⁷⁹ To integrate the quantitative and qualitative results, we will follow guidelines for best practices in mixed methods⁸⁰ as well as our previous experiences with mixed methods implementation research.⁸¹⁻⁸⁴

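### Clinic adaptive reserve rests on about 1.8 to at most 2.5 PCP responses per clinic with no reliability step, so path b and a × b may be attenuated although the plan calls the product unbiased

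*Protocol*

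**What the plan says.** The current protocol's list of primary outcome variables names "Aim 2. Staff-reported clinic adaptive reserve". The only instrument described for it is the PCP survey, whose Aim 2 mediator items cover "clinic-level adaptive reserve and PCP motivation to implement" the program (Methods, Study Instruments). No survey of other clinic staff is described.

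On numbers, Target Population and Accrual says "There are currently 137 pediatric physicians and 14 non-physician PCPs (N = 151) in the two systems" and "We expect response rates of 50% at each of these two time points". One survey falls before the strategies start and one during active implementation.

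The Aim 2 Analysis tests mediation by product of coefficients in a 2-2-1 model, with path b described as "the relationship between the clinic-level mediator (i.e., adaptive reserve) and the three binary reach outcomes (counseling, cable lock, both"). It states that "we will have approximately 76 PCPs and 20 clinics per study arm", gives a detectable indirect effect of d = .44, calls that calculation conservative because it leaves out the second time point, and calls a × b unbiased. It gives no rule for forming the clinic value, no minimum number of respondents, no rater ICC and no reliability step. Motivation is to be analysed in the same way as an exploratory mediator.

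The number of clinics differs between sections. The Aim 1 Analysis says "expect to include data from 151 PCPs, within 41 clinics". The introduction says "all 30 clinics in the two participating health systems will receive" the program materials, and the SAP's balance check also uses 30 clusters. The SAP's analysis plan covers only the primary reach comparison, so the protocol's Aim 2 Analysis is the only mediation specification.

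**The concern.** Adaptive reserve is a property of the clinic, but its value would come from about two individuals. A mean of two ratings carries rater noise. If that noisy mean is the regressor in path b, classical error pulls b towards zero, pulls a × b down in the same proportion, and moves the missing part into the direct effect. Path a is not biased in raw units, only less precise. The joint significance test needs both paths to be significant, so facilitation could work through adaptive reserve and still be reported as not doing so. The plan's description of a × b as unbiased would encourage that reading of a null result.

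**Working it through.** **The plan's own figures.** 151/2 = 75.5 and 41/2 = 20.5 reproduce the stated 76 PCPs and 20 clinics per arm, so the mediation sample counts every PCP. At 50% response, one survey wave gives about 38 per arm. The d = .44 cannot be reproduced properly, because the power, the path sizes and the mediator ICC are not stated. Simple two-group versions with 76 per arm give:
- Two-sided, no clustering: power 77.4% at d = .44; detectable d at 80% power is .454.
- Two-sided, design effect 1 + (3.8 − 1) × .07 = 1.196: power 69.9%; detectable d is .497.
- One-sided with the same design effect: detectable d is .441. This matches only against the two-sided alpha stated for Aim 1, and it is not an indirect-effect formula.

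**Responses per clinic per wave.**
- 41 clinics: 151/41 = 3.68 PCPs; × 0.5 = 1.84 responses.
- 30 clinics: 151/30 = 5.03; × 0.5 = 2.52. This is an upper figure, because 151 counts PCPs in both systems and the number working in the 30 trial clinics is not given.
- Chance of no respondent at average clinic size: 0.5^3.68 = 7.8% (about 3 of 41 clinics) or 0.5^5.03 = 3.1% (about 1 of 30).

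**Reliability of the clinic mean.** With k responses, reliability = k × ICC / (1 + (k − 1) × ICC). Under classical error this is the share of b that is kept. The ICC of adaptive reserve is an assumption throughout; the plan's only ICC, .07, belongs to the Aim 1 power calculation for reach.

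| Assumed ICC | k = 1.84 | k = 2.52 |
|---|---|---|
| .07 | .12 | .16 |
| .20 | .32 | .39 |
| .30 | .44 | .52 |
| .50 | .65 | .72 |

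Reliability of .70 would need an ICC of about .56 (k = 1.84) or .48 (k = 2.52).

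**A narrower target.** If the clinic value means only the average view of the clinic's own n PCPs, half of whom respond, the factor is (ICC + (1 − ICC)/n) / (ICC + (1 − ICC)/(n/2)). With n = 3.68 it is .56, .66, .72 and .82 at ICC .07, .20, .30 and .50. With n = 5.03 it is .58, .69, .76 and .86.

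**Simulation check.** A linear clinic-level model was run with 3,000 replicates per setting. It assumed a = 0.8 SD, a partial correlation of .5 for path b, no true direct effect, varying clinic size and 50% response.

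| Clinics | ICC | Share of b kept | Spurious direct effect | Joint-test power, true → observed mediator |
|---|---|---|---|---|
| 40 | .07 | 11% | .41 | 64% → 2% |
| 40 | .20 | 29% | .32 | 62% → 7% |
| 40 | .30 | 42% | .26 | 63% → 13% |
| 40 | .50 | 63% | .18 | 64% → 28% |
| 30 | .07 | 13% | .41 | 47% → 2% |
| 30 | .20 | 34% | .30 | 45% → 6% |
| 30 | .30 | 47% | .25 | 46% → 11% |
| 30 | .50 | 66% | .15 | 44% → 21% |

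The simulated b falls slightly below the formula because respondent numbers vary between clinics. Path a stays near 0.8.

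**The case against.** Several stronger readings are tempting, and the documents do not support them.

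- **That the plan treats the mediator as error-free.** It does not say so. This would be inferred from the 2-2-1 label and the silence on correction. MPlus, the named software, can fit a latent clinic mean. What is established is an omission.
- **That the attenuation is necessarily strong.** No rater ICC for adaptive reserve is given. At ICC .50 the loss is 28% to 35%, and under the narrower target it is smaller still. That target is a reasonable reading, above all for motivation, which is a PCP attribute.
- **That the plan calls the effect estimate conservative.** That word describes the power calculation. Unbiased is the word applied to a × b. The power argument gains little, since the baseline survey precedes the strategies and adds no responses to the post-strategy clinic mean.
- **That bias must be towards zero.** PCPs supply both the adaptive-reserve ratings and the EHR-documented reach. Error shared between the two could raise b.
- **That a null mediation result would be caused by measurement.** Under the assumed large paths, a perfectly measured mediator gives only 44% to 47% joint-test power with 30 clinics, so a null is likely anyway.
- **That the corrected model should replace the main one.** At reliability .12 to .16, correction multiplies b about 6 to 8 times (1/.16 to 1/.12). In simulation with 30 clinics, correction roughly restored the median of b at ICC .10 and above. However, root mean squared error rose from .40 to 2.0 at ICC .20, and the estimated reliability was near zero in 17% of runs at ICC .20 and 41% at ICC .07.

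All of these limits stand. They leave in place the small number of responses per clinic, the missing reliability information and the unsupported claim of unbiasedness. The staff-reported label is a minor wording matter.

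**Conclusion.** The concern holds as a specification gap with a possible bias whose size the documents do not fix. On the protocol's own response rate, clinic adaptive reserve rests on about 1.8 responses per clinic, or at most 2.5. Under classical error and an assumed ICC of .07 to .50, b and a × b keep about 12% to 72% of their size. If the target is only the clinic's own PCPs, the range is about 56% to 82% on 41 clinics (58% to 86% on 30). Shared-reporter error could offset or reverse this. Without a stated rater ICC, neither a large nor a negligible loss can be asserted, but calling a × b unbiased is not justified. The randomised Nudge versus Nudge+ comparison is unaffected. The point bears on how Aim 2 is interpreted.

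**What to change.** In the protocol's Aim 2 Analysis:

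1. Remove the description of a × b as unbiased.
2. State that the main 2-2-1 model uses the observed mean of the responding PCPs, and how clinics with no respondent are handled. Align the staff-reported label with the PCP survey.
3. Report the rater ICC and the clinic-mean reliability of adaptive reserve.
4. Add a prespecified sensitivity analysis, either a latent clinic mean in MPlus or a reliability-corrected path b, shown beside the raw estimate with its interval.
5. State that a non-significant path b with low reliability will not be read as evidence that facilitation does not act through adaptive reserve.

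The cost is wording and one extra model in software already named; no new data are needed. The corrected estimate will be imprecise with 30 clinics and may fail when the estimated reliability is near zero. That is why it belongs in a sensitivity analysis.

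### Aim 2 mediation: the reach window closes before the mediator is measured, and the power statement counts 20 clinics per arm where the trial has 15

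*Protocol*

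**What the plan says.** The Protocol's list of primary outcome variables gives, for Aim 2, "Staff-reported clinic adaptive reserve". Study Instruments places it in the PCP survey: "Aim 2 mediator measures will also ask about PCP attitudes and experiences (e.g., clinic-level adaptive reserve and PCP motivation to implement" the program. There are two such surveys, one before and one during implementation, and "Each of the surveys will include questions related to some or all of the following constructs", so collection of adaptive reserve at baseline is not certain.

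The Aim 2 Analysis defines path a as strategy to adaptive reserve and path b as adaptive reserve to reach. Reach is timed thus: "We will calculate change in reach for each of the two time-points using the 6 month period preceding each survey administration". It continues: "An unbiased estimate of the mediated effect is derived via the product of the" two paths.

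On power it says "we will have approximately 76 PCPs and 20 clinics per study arm", that this is sufficient for an indirect effect of d = .44, and "We assume there will be a large effect of the strategy on the mediator and of the mediator on the outcome". It calls the figure conservative because "the calculation does not account for the additional power that will be gained due to the two measurement time-points for each PCP".

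The SAP covers only the primary comparison of Nudge and Nudge+, so it neither repeats nor amends any of this.

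**The concern.** A mediation claim needs the mediator to come before the outcome. Here the outcome window ends when the mediator is measured. If clinics where delivery went well early then rate themselves higher, path b will be positive even if adaptive reserve does nothing for reach. Facilitation that raised early reach would then yield a significant product of paths and an unsupported mechanism claim.

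The outcome is also unclear. Two windows give one change, not a change for each time-point, and the first window precedes implementation, for which no reach measure is defined.

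On power, a null mediation result could be read as adequately powered on a clinic count that the trial does not have. Identifying mediators is a named aim, so both errors would affect a main conclusion of Aim 2. The Aim 1 comparison is not affected.

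**Working it through.** **1. Order of measurement.** Adaptive reserve is read at the survey date; reach is counted over the six months before it. Only the implementation survey can carry an effect of the randomised strategy. On the protocol's Timeline it sits in the third of four facilitation quarters, so its reach window covers roughly the first two. The order is mediator last, while path b is specified as mediator first.

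**2. Change in reach.** The SmartList is on from implementation through sustainment (Detailed Description, Nudge), and the Aim 1 Analysis uses reach only in the active and sustainment periods. Pre-implementation EHR extraction is planned, including firearm-storage and cable-lock documentation (Data Collection), and the SAP's amendment rationale reports EHR reach for October 2021 to February 2022 without naming the clinics. Some pre-launch documentation therefore exists, but no baseline reach measure is defined for the trial clinics.

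**3. Source of the power inputs.**
- 41/2 = 20.5 and 151/2 = 75.5 give the stated 20 clinics and 76 PCPs. The Aim 1 Analysis has 151 PCPs in 41 clinics.
- The Protocol introduction, the 08 March 2022 amendment entry and the SAP balance check give 30 clinics: 30/2 = 15 per arm.
- Expected PCP response is 50% per survey (Target Population and Accrual): 151 × 0.5/2 = 37.75 respondents per arm. If PCPs fell in proportion to clinics (assumption): 151 × (30/41) × 0.5/2 = 27.6.
- But 151 × 0.5 = 75.5 as well, so 76 could be total respondents.

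**4. The stated d = .44.** No path values, mediator ICC or power level are given, so it cannot be reproduced. As a plain two-group comparison with 76 per arm, 3.8 PCPs per clinic and ICC .07 (Aim 1's value), the design effect is 1 + 2.8 × .07 = 1.196 and the effective n is 76/1.196 = 63.5. The effect detectable at 80% power is then 0.50 two-sided and 0.44 one-sided. The one-sided match is not a mediation calculation and contradicts the two-sided alpha stated for Aim 1.

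**5. Path a (illustration).** I take large to mean d = 0.8, two-sided .05, noncentral t with 2k − 2 df, k clinics per arm.

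*Clinic means* (d in SDs of clinic means). The SE ratio is √(20/15) = 1.155. The noncentrality is 0.8 × √(k/2): 2.53 at k = 20 and 2.19 at k = 15. Power is 69% and 56%.

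*PCP scale* (d in SDs of individual ratings), with m respondents per clinic: SE = √[ICC + (1 − ICC)/m] × √(2/k). ICC .07 is borrowed from Aim 1; .3 is a second assumption.

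| Per arm | m | ICC .07: SE, power | ICC .3: SE, power |
|---|---|---|---|
| 20 clinics, 76 respondents | 3.80 | 0.177, 99% | 0.220, 94% |
| 20 clinics, 38 respondents | 1.90 | 0.237, 91% | 0.259, 85% |
| 15 clinics, 37.75 respondents | 2.52 | 0.242, 89% | 0.278, 79% |
| 15 clinics, 27.6 respondents | 1.84 | 0.277, 80% | 0.301, 73% |

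Row 1 to row 3 is the loss if 76 is per arm before non-response; row 2 to row 3 is the loss if 76 is total respondents.

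**6. Does moving the window suffice?** Simulation at clinic level, 4,000 runs per setting, under these assumptions: 15 clinics per arm, true path b of zero, strategy effect on early reach d = 0.8, early reach to rating 0.5, early-to-late reach correlation .5, .7 or .9. Path b is falsely significant in:
- pre-survey window: about 81% of runs;
- post-survey window, no adjustment for earlier reach: 26%, 47% and 71%;
- post-survey window, adjusted for pre-survey reach: about 5%.

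**The case against.** **Adaptive reserve may be a slow trait**, so that a mid-year rating stands for the preceding months. The documents give no recall frame, so the size of any reverse influence is unknown, and a reader should not infer that it is large or certain. But the plan expects facilitation to change adaptive reserve strongly within the year, which sits badly with treating it as fixed. The order of measurement stands.

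**The word unbiased may describe the multilevel estimator**, as the sentence cites methods papers that are not available here. That is possible. The text does not limit itself to that sense, so the wording needs narrowing.

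**Baseline reach may be obtainable.** A reader might infer that no pre-launch reach can exist because the SmartList was not on. The documents do not support that: extraction is planned and some pre-launch EHR reach is reported. What is missing is a definition for the trial clinics.

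**The 76 PCPs.** It is tempting to say that respondents drop from 76 to 38 per arm. That is the more literal reading, but 151 × 50% is also about 76, and the accrual section's counting is loose: it reaches a survey target of 151 PCPs from 50% response at two surveys. On the second reading the SE of path a rises only about 2% (ICC .07) or 7% (ICC .3), against 36% or 26% on the first. Non-responders also still contribute EHR reach; only the mediator is thinned.

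**The d of .44.** A reader might infer that it is wrong. That cannot be shown, because its inputs are not stated, and path a power stays near 80% or above in several rows of the table.

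**Conclusion.** Two points hold from the text alone. The reach window precedes the mediator it is meant to follow, so path b does not identify an effect of adaptive reserve on reach. And 20 clinics per arm contradicts the trial's 30 clinics, which raises the clinic-level SE of path a by about 15%; power on clinic means falls from 69% to 56% if large means d = 0.8.

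The change-in-reach outcome cannot be coded as written. The PCP-scale loss depends on an unresolved reading: 99% to 89% or 94% to 79% if 76 is per arm before non-response, and 91% to 89% or 85% to 79% if it is total respondents (ICC .07 and .3, both assumed). The conservative label is unsupported at least because of the lost clinics, whichever reading of 76 is right.

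**What to change.** - Use implementation-survey adaptive reserve as the mediator and visit-level EHR reach after that survey as the outcome. Adjust for reach in the active period before the survey, and for baseline adaptive reserve if it was collected. Step 6 shows that moving the window without the reach covariate leaves much of the problem.
- State that pre-survey reach is itself post-randomisation, so the result still rests on assumptions, and do not call it unbiased.
- Add a sensitivity analysis limited to visits between the actual survey date and the end of facilitation in month 12. Keep the pre-survey-window model only as a secondary analysis labelled associational.
- Replace the change-in-reach sentence with the definition above.
- Restate the inputs as 15 clinics per arm with expected respondents per arm per survey, and say what 76 meant. Recompute the detectable indirect effect with path values, mediator ICC and power level stated. Remove the conservative label.

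The 41-versus-30 conflict runs through the protocol and should be reconciled once.

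Cost: wording and a recalculation, with no new data collection, since EHR reach continues into sustainment. The power figure will be less favourable, and part of the post-survey window may fall after facilitation ends. How much depends on the actual survey date, which the documents do not give.
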